14.7 Sample Size

In a previous study²⁵, 275 relapses on 106 patients were observed, corresponding to a mean number of relapses per patient of 2.6 (Standard deviation, SD: 0.7) while in the post-treatment group 36 relapses were registered corresponding to a mean number of relapses per patient of 0.34 relapses/patient. With a statistical power of 80% and a significance level (alpha) of 5% and a common SD of 0.7, 46 patients are needed to observe a difference of 0.6 relapses/patients between the two treatment groups (i.e., 2 relapses/patient in the NORFLO[®] ORO treatment group vs. 2.6 in the placebo treatment group). To take into account a potential dropout rate of 20% over 12 months, 60 patients will be recruited. Subjects dropping out the study because they are beginning systemic therapy with anti-inflammatory, immunosuppressive, biologic drugs will be replaced.

A second primary endpoint, i.e. the reduction of mean number of relapses between the year before treatment and the study period, will be examined. No formal sample size estimate is feasible on this endpoint, as it was not tested previously and no reasonable scenario can be drawn.

As the two endpoints will be assessed in a hierarchical order (first, "the mean number and intensity of relapses during the study between treatment groups" and then "the reduction of mean number of relapses between the year before treatment and the study period"), according to the "Points to consider on multiplicity issues in clinical trials", issued by the Committee for Proprietary Medicinal Products (CPMP - 2002), no sample size adjustment for multiplicity is needed.

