# 7. SAMPLE SIZE AND STATISTICAL POWER CONSIDERATION

With a statistical power of 80% and a significance level (alpha) of 5% and a common SD of 0.7, 46 patients are needed to observe a difference of 0.6 relapses/patients between the two treatment groups (i.e., 2 relapses/patient in the NORFLO® ORO treatment group vs. 2.6 in the placebo treatment group). To take into account a potential dropout rate of 20% over 12 months, 60 patients were recruited.

A second primary endpoint, i.e. the reduction of mean number of relapses between the year before treatment and the study period, will be examined. No formal sample size estimate was feasible on this endpoint, as it was not tested previously and no reasonable scenario can be drawn.

As the two endpoints will be assessed in a hierarchical order (first, "the mean number and intensity of relapses during the study between treatment groups" and then "the reduction of mean number of relapses between the year before treatment and the study period"), according to the "Points to consider on multiplicity issues in clinical trials", issued

Statistical Analysis Plan Version no. 1.0 – 20/07/2020 Protocol Code NORFLO-ORO-16 EudraCT number NA

by the Committee for Proprietary Medicinal Products (CPMP - 2002), no sample size adjustment for multiplicity was needed.

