### Multiple Comparisons and Multiplicity 9.3

No adjustment for multiple comparisons will be done. Even if multiple primary endpoints will be analyzed, no adjustment for multiplicity will be done, as the primary efficacy endpoints will be analyzed in the following hierarchical order; first, "the mean number and intensity of relapses during the study between treatment groups" and then "the reduction of mean number of relapses between the year before treatment and the study period".

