### 11. EFFICACY ANALYSIS

SAS 9.4 for windows (SAS Institute Inc., Cary, NC, USA) will be used for statistical analysis. A level of statistical significance (alpha) of 5% will be used to evaluate statistically significant differences between the two treatment groups, placebo and active treatment. Parametric tests will be used as the first-choice test. When the dependent variables are not normally distributed, also the non-parametric alternative will be used.

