## 11.4 Efficacy Analysis

## 11.4.1 Primary Efficacy Endpoints

The number and intensity of relapses were assessed through instrumental analysis and physical examination. These endpoints will be assessed from baseline to end of treatment.

When a relapse occurs, the data reported in the first unscheduled visit concerning the intensity of the relapse and data from LFM will be used as they are taken before the administration of both systemic and topical cortisone.

Mean and standard deviation will be used to describe the number of relapses per patient. The mean number of relapses per patient will be compared between the treatment groups using Student's t-test. ANOVA will be used to include predictive/confounding variables in the model.

In addition, a generalized linear mixed model (GLMM) with Poisson statistical distribution and with the number of relapses as dependent variable will be used to assess the effects of the treatment on reducing the number of relapses, also including in the model other potentially predicting/confounding variables.

The intensity of each relapse will be scored as mild (either trace to 1+ cell OR flare  $\leq 20$ ), moderate (2+ to 3+ cell OR Flare  $\geq 20$  and  $\leq 100$ ) and severe (4+ cell OR Hypopyon OR flare  $\geq 100$ ). For each patient, the average intensity will be estimated as the mean of the intensity of relapses observed during the study. The average and the maximum intensity will be compared between treatment groups using Student's t-test. ANOVA will be used to include predictive/confounding variables in the model. As this variable could likely be not normally distributed, Wilcoxon Mann-Whitney will be also used.

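### Maximum relapse intensity is tested without regard to the number of relapses, so a product that only lowers frequency can appear to lower severity

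*SAP*

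**What the plan says.** Each relapse is graded mild, moderate or severe (SAP 11.4.1; Protocol 14.3). Two summaries are then formed per patient, the mean grade and the worst grade. "The average and the maximum intensity will be compared between treatment groups" by Student's t-test, with ANOVA for unnamed covariates; the SAP adds a Wilcoxon test.

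SAP 9.3 ranks first "the mean number and intensity of relapses during the study between treatment groups" and makes no multiplicity adjustment. SAP 5.1 limits the primary analyses to patients who relapsed. SAP 7 plans for 2 relapses per patient in the active "treatment group vs. 2.6 in the placebo treatment group". The primary objective (Protocol 3.1, SAP 3.1) names frequency and severity as two things to be reduced.

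No text adjusts the maximum for the number of relapses or says how the average and the maximum together decide the severity question.

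**The concern.** The worst of three draws from one severity distribution tends to exceed the worst of two. If the product prevents relapses but leaves each remaining relapse unchanged, placebo patients will still show higher maxima. The test on the maximum then measures frequency a second time under the name of severity. A reader of the report could take it as independent support for the frequency result, or as evidence for the severity half of the objective, when it is neither. The better the product prevents relapses, the stronger the effect.

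**Working it through.** **Inputs from the documents.** "A level of statistical significance (alpha) of 5% will be used" (SAP 11). Planned effect: "a difference of 0.6 relapses/patients between the two treatment groups", SD 0.7 (SAP 7). Thirty per arm (SAP 4.2). Relapsers only (SAP 5.1).

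**Inputs assumed.** Grades coded 1/2/3; two-sided test; independent severities within patient unless stated; count distribution; severity mix. The documents give no mix. Protocol 2 reports only mean flare 160 ± 22 ph/ms, range 11-787, in 44 acute cases. The mild/moderate/severe mixes tried were equal thirds, 50/35/15, 60/30/10, 20/50/30, 80/15/5, 10/30/60, 50/30/20 and 1/40/59.

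**The plan's own figure.** n per arm = 2(1.960 + 0.842)² × 0.7² / 0.6² = 21.4, so 22 (44 in all) by the normal approximation. The t-based solution is 22.37, so 23 per arm, which gives the 46 in SAP 7. With 20% dropout, 46/0.8 = 57.5, or 58; 60 are planned. The inputs are read as intended.

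**Mechanism.** With mix 50/35/15, a patient with k relapses has P(max ≤ 1) = 0.5^k and P(max ≤ 2) = 0.85^k, so E[max] = 3 − 0.5^k − 0.85^k.

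| k | E[max] | E[average] |
|---|---|---|
| 1 | 1.65 | 1.65 |
| 2 | 2.03 | 1.65 |
| 3 | 2.26 | 1.65 |

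For Poisson counts with mean λ among relapsers, E[0.5^K] = (e^(−0.5λ) − e^(−λ))/(1 − e^(−λ)) and E[0.85^K] = (e^(−0.15λ) − e^(−λ))/(1 − e^(−λ)).
- λ = 2.0: 3 − 0.269 − 0.700 = 2.031.
- λ = 2.6: 3 − 0.214 − 0.651 = 2.135.
- Spurious difference: 0.104 points, with identical severity in both arms.

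**Rejection rates.** Simulation of 3,000 to 8,000 trials per scenario, identical severity in both arms, pooled t-test on patient maxima, 30 per arm. With equal counts (2.6 v 2.6) the test rejects in 4.7-5.3%, as it should.

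| Counts, 2.0 v 2.6 | Maximum rejects |
|---|---|
| SD 0.7 | about 9-15% |
| Poisson | about 6-9.5% |
| Overdispersed (negative binomial, k = 1) | about 5-7% |

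- Most of the rejections favour the product: in one set of runs 8.3-13.4% (SD 0.7) and 6.2-7.6% (Poisson), against 2.5% nominal in that direction.
- Wilcoxon does not cure it: 12.1-12.9% (SD 0.7), 7.4-8.5% (Poisson).
- Within-patient severity correlation of 0.5 (mix 50/35/15): 8.1% (SD 0.7), 6.6% (Poisson).
- Average intensity in the same scenarios: 4.4-5.7%, mean difference about 0.

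**Larger frequency effects, independent severities.** At 1.3 v 2.6 the maximum rejects in 37-42% (SD 0.7), 16-21% (Poisson) and 11% (overdispersed). Protocol 14.7 cites an earlier post-treatment "mean number of relapses per patient of 0.34 relapses/patient". At 0.34 v 2.6 the rates are 45-54%, 30-35% and 24-25%, falling to 22% (SD 0.7) and 15% (Poisson) with correlation 0.5. Not all of that last excess is due to the count link: the average also rejects in 9-10% there with independent severities, because one arm has few relapsers and the variances differ.

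**Combining the two summaries at 2.0 v 2.6.** If either significant test were enough, severity would be falsely declared in about 10-17% of trials (SD 0.7 or Poisson counts). Part of this is ordinary multiplicity, since two tests at 5% allow up to 5% + 5% = 10% anyway. If both were required, the rate is about 2-3%.

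**The case against.** A reader might infer that the error rate is far above 5% as a general matter. The documents do not support that. The highest rates at the planned effect come from counts with SD 0.7. The SAP's own count model is Poisson, which gives roughly half the excess, and overdispersion or correlated severities reduce it further.

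A reader might also infer that a significant maximum by itself earns a severity claim. The SAP does not say so. The maximum appears only in the methods text, not in the endpoint definition (SAP 5.1), the hierarchy (SAP 9.3) or the summary table (SAP 11.5). If both tests had to succeed there would be no inflation. This stands, and it makes the missing combination rule part of the problem.

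Third, the worst attack per patient is a legitimate quantity, and a product that prevents attacks does lower it. The test is valid for that quantity. But the objective sets severity beside frequency as a separate aim, and for that aim this comparison is not informative on its own. Testing the average alongside would often expose the pattern, but only to a reader who knows to look.

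Fourth, the withdrawal rules (Protocol 7.1 and 10.4) truncate counts. With 59% severe relapses, latent means of 2.0 and 2.6 would be observed as about 1.4 and 1.5, so that mix cannot coexist with observed means of 2.0 and 2.6. Stopping at a severe relapse nevertheless leaves the rejection rate for the maximum essentially unchanged, because the top score is already reached. It does give the average a small link to the count: about 0.02-0.05 points, with rejection about 5-7%. The average is therefore nearly, not wholly, free of the count.

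Finally, the objective is worded as exploratory, so a caveat might seem enough. Since the endpoint is formally ranked and the change is only one of wording, that is a weak reason to leave the text as it is.

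**Conclusion.** The point holds in moderate form. The maximum is compared between arms under the first-ranked endpoint with no allowance for relapse count, and a frequency-only product can be credited with lower severity. At the planned effect the excess over 5% ranges from negligible (overdispersed counts) to about 10 percentage points (SD 0.7 counts). It is larger if relapses fall by more than planned and smaller with within-patient correlation. These sizes rest on the assumed coding, two-sided test, severity mixes, count distributions and, unless stated, independent severities. The direction of the bias needs none of the particular mixes. How often a false severity claim would be made cannot be fixed from the documents, because the rule for combining average and maximum is absent. The text should be changed before analysis.

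**What to change.** In SAP 11.4.1, with SAP 13 recording the departure from Protocol 14.3:
- Report maximum intensity descriptively, tabulated by number of relapses, and state that it will not be used as evidence of a severity effect.
- Base the severity test on average intensity per patient, or on a per-relapse ordinal mixed model with a patient random effect, and name which one decides.
- State how the number and intensity results combine within the first rank.
- Note that withdrawal after a severe relapse leaves a small link between average intensity and relapse count.

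The cost is SAP wording. No data are lost, and the worst-attack summary stays in the tables but is no longer a tested result. The simulations above cover the average; the operating characteristics of the per-relapse model at this sample size would need checking if it is chosen.

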10.4 Additional Unscheduled Visits in Case of Relapse

Should a relapse occur, an unscheduled visit will be performed including a complete ophthalmic evaluation. The number of cells in the AC will be determined by slit lamp, too.

Topical or systemic treatment will be prescribed to the subject according to the severity of the relapse and according to the best medical judgement.

Two following visits will be scheduled 2 and 6 weeks thereafter. During these visits a complete ophthalmic evaluation will be done.

If the subject is prescribed a systemic treatment for the relapse, he/she will be withdrawn from the study, and treated according to the best medical judgement.

If only topical treatments are prescribed, the subject will be allowed to continue the study. Depending on the onset time of the relapse it could be necessary to delay Visit 2 or Visit 3 around 2 months after the topical treatment conclusion.

Should Visit 2 be delayed, the delay will be recovered by keeping the date of Visit 3 at 12 months.

Should Visit 3 be delayed, the delay will not be recovered.

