### 4.3 Randomization and Blinding

Up to 60 eligible patients were randomly assigned to NORFLO® ORO or placebo treatment groups in a 1:1 ratio rusing a stratified randomization-blocks-scheme. The patient randomization list was generated-by-Latis S.r.l., using the procedure PROC PLAN of SAS 9.4 for Windows (SAS Institute Inc., Cary, NC, USA).

Due to the objectives of the study, the investigators, research staff, or patients did not know the treatment identity (test or control). The following study procedures were in place to ensure double-blind administration of study treatments:

Access to the randomization code was strictly controlled.

Packaging and labeling of test and control treatments were identical to maintain the blind.

The study blind will be broken on completion of the clinical study and after the study database has been locked.

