The mean number of relapses per patient observed during the study will be compared to the mean number of relapses reported the previous year within each treatment group using paired t-test. The patients will be classified based on the number of relapses before treatment, using the median number per subjects as a cut-off to separate subjects with a high number of relapses form those with a low number of relapses. The subjects will be classified on the number of relapses after treatment using the same cut-off. The patients that before and after treatment will change from the high number of relapses category to the low number category, will be considered as responders, while the others will be considered as non-responders. The proportion of responders will be compared between treatment groups using chi-square test.

The primary efficacy endpoints will be analyzed in the following hierarchical order: first, "the mean number and intensity of relapses during the study between treatment groups" and then "the reduction of mean number of relapses between the year before treatment and the study period".

The level of cell damage and inflammation will be assessed through Laser Flare Meter. The difference between treatment groups will be compared using ANCOVA, with the baseline level included in the model.

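### The SAP responder rule keeps patients who cannot respond in the denominator and, with no rule for withdrawal, can score a relapse-driven withdrawal as a success

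*SAP*

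**What the plan says.** SAP 11.4.1 follows the within-arm before/after comparison with a responder analysis. Patients are classified on the prior-year count "using the median number per subjects as a cut-off to separate subjects with a high number of relapses" from the rest. The same cut-off is applied to the on-study count. Those who move from high to low "will be considered as responders, while the others will be considered as non-responders", and the proportions are compared between arms by chi-square. The section does not say on which side a count equal to the median falls, whether the median is taken over the pooled arms, or what to do when follow-up is incomplete.

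Other sections decide what count enters the rule:

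- Protocol 10.4: "If the subject is prescribed a systemic treatment for the relapse, he/she will be withdrawn from the study". Protocol 7.1 has the subject leave the study when flare exceeds 100 ph/ms.
- SAP 9.1.4 replaces no missing data. After study treatment is stopped, the remaining visits are encouraged but not required.
- SAP 8.1 and 11.1 admit to the efficacy population any eligible dosed patient with a post-randomization endpoint estimate. A patient seen at a relapse visit has one.
- SAP 5.1 restricts the primary endpoint analyses to patients with relapses.
- The responder proportion appears neither in the hierarchy (SAP 9.3) nor in the summary of efficacy analyses (SAP 11.5).

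**The concern.** Protocol 14.3 introduces the classification because group means can mislead when events are few, so a reader will use it as a check on the main result. As defined, it can mislead in two ways.

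First, a patient who starts in the low category scores the same whether he or she has no relapse on study or five. Such patients carry no information about treatment but stay in the denominator.

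Second, a patient with four relapses in the prior year who is withdrawn at the first on-study relapse, because it needs systemic treatment, has a recorded count of one. With a cut-off of two or three that is low, so a treatment failure is scored as a response. The arm with more such withdrawals gains responders.

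**Working it through.** **The plan's own figure.** SAP 7 sets the design inputs: "With a statistical power of 80% and a significance level (alpha) of 5% and a common SD of 0.7". The assumed effect is a fall from 2.6 relapses on placebo to 2 on active, and the resulting total is 46. Allocation is "placebo treatment groups in a 1:1 ratio"; sidedness is not stated, and two-sided is assumed. The noncentral t gives power 79.3% at 22 per arm and 81.1% at 23, so 46 is reproduced. For the "potential dropout rate of 20% over 12 months, 60 patients were recruited", 46/0.8 = 57.5, that is 58, close to 60. No figure is given for the responder comparison.

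**Assumptions.** Integer counts (discretised normal shape) matched to the planning figures: baseline at least 1 (inclusion criterion 3), mean 2.6, SD 0.7 (Protocol 14.7); on study, mean 2.0 (active) or 2.6 (placebo), SD 0.7. Baseline and on-study counts are independent. Each relapse leads to withdrawal with probability s, the same in both arms; s is not in the documents.

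**Who can respond.** The fitted baseline puts 4.3%, 39.6%, 48.3% and 7.7% of patients at 1, 2, 3 and 4 relapses, so the median is 3.

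- High means 3 or more: 56% are high and 44% cannot respond.
- High means more than 3: 8% are high and 92% cannot respond.

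A more dispersed baseline (zero-truncated Poisson with parameter 2.6: mean 2.8, SD 1.5), with the median taken from 60 patients, gives about 38% and 62-63%. The 2.6/0.7 shape with a median from 60 patients gives 37% and 84%.

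**Effect of withdrawal, high = 3 or more.** Let h = 0.562 be the share high at baseline and q the chance of 3 or more relapses with full follow-up: 0.215 active, 0.563 placebo. A high-baseline patient stays high only by reaching a third relapse without withdrawal at the first or second. Hence:

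- SAP rule: responders = h × [1 − q(1 − s)²].
- Difference = h × (0.563 − 0.215) × (1 − s)² = 19.5 points × (1 − s)².
- Withdrawal counted as non-response: responders = h × Σ P(y)(1 − s)^y over y = 0, 1, 2, where P(y) is 0.010, 0.206, 0.569 (active) and 0.001, 0.042, 0.395 (placebo). Dividing by h gives the proportion among high-baseline patients.

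| s | Withdrawn, active/placebo | SAP rule, active/placebo | Difference | Withdrawn = non-responder, all | Same, high baseline only |
|---|---|---|---|---|---|
| 0 | 0/0% | 44.1/24.6% | 19.5 | 44.1/24.6% | 78.5/43.7% |
| 10% | 19/24% | 46.4/30.6% | 15.8 | 36.9/20.1% | 65.6/35.8% |
| 20% | 35/43% | 48.4/35.9% | 12.5 | 30.3/16.1% | 53.9/28.7% |
| 30% | 49/59% | 50.3/40.7% | 9.6 | 24.3/12.5% | 43.3/22.3% |

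**Power**, from Φ{[|p₁ − p₂|√n − 1.96√(2p̄(1 − p̄))] / √[p₁(1 − p₁) + p₂(1 − p₂)]}, with n = 30 per arm, or 30 × 0.562 ≈ 17 when restricted. The three columns are SAP rule, withdrawn as non-responder in all patients, and the same among high-baseline patients only:

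| s | SAP rule | All | High only |
|---|---|---|---|
| 0 | 35% | 35% | 55% |
| 10% | 24% | 30% | 40% |
| 20% | 16% | 25% | 31% |
| 30% | 11% | 21% | 25% |

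**Direction.** If s differs by arm, the difference is h × [0.563(1 − s_placebo)² − 0.215(1 − s_active)²]. With s = 10% on active and 30% on placebo: 0.562 × (0.276 − 0.174) = 5.7 points. Reversed: 0.562 × (0.456 − 0.105) = 19.7 points. The error moves towards whichever arm loses more patients per relapse.

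**Patients without relapse.** At the planning rates they are about 1% or fewer. At the earlier study's post-treatment mean of 0.34 (Protocol 14.7), a Poisson count gives e^(−0.34) = 0.71, so about 21 of 30 active patients would be left out if SAP 5.1 applies here, although they are the clearest successes.

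**The case against.** The case against is substantial.

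- **Low-baseline patients.** The category is fixed before treatment and balanced by randomization, so the test stays valid under no difference. A reader might infer that the whole comparison is biased; for this part it is only diluted. This stands.
- **Scoring of withdrawn patients.** A reader might infer that the SAP declares withdrawn patients to be responders. It does not. That follows from using the raw count with no follow-up rule, and only for high-baseline patients whose count is still below the cut-off. If the median were 1 and high meant 1 or more, a patient withdrawn at one relapse would stay high. This limits the point but does not remove it. Encouraged visits after stopping treatment are no remedy, because Protocol 10.4 withdraws the patient from the study.
- **Severe is not the same as withdrawn.** 4+ cells or hypopyon need not lead to systemic therapy, and flare of exactly 100 ph/ms is severe but not above 100. The documents do not support saying that every severe relapse is scored as a success.
- **Withdrawal rate.** A reader might infer that most responders would be withdrawn patients. That needs rates near the top of the range: s = 30% means 49% and 59% of patients withdrawn, against a planned dropout of 20%. At s = 10% the figures are 19% and 24%. Protocol 11.2 also replaces patients who drop out for systemic therapy, so 30 per arm is approximate; nothing says that the replaced patients leave the analysis.
- **Weight.** The analysis is outside the hierarchy and the summary table, and no sample size rests on it. This stands.

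**Conclusion.** The point holds for a supportive analysis. By construction, low-baseline patients cannot respond; they dilute both arms without favouring either, and how many there are turns mainly on an unstated tie rule (about 37-44% against about 62-92%). Separately, relapse-driven withdrawal can be scored as response. With equal withdrawal per relapse in both arms, a true difference of about 20 points shrinks to about 16 at 10% and about 10 at 30%; with unequal withdrawal the shift can go either way. The sizes rest on the fitted count distributions, independence of baseline and on-study counts, a cut-off of 3 with high at or above it, and assumed withdrawal rates. No confirmatory conclusion of the trial depends on this comparison, but its defects should be removed because it is a formal between-arm test reported under the primary endpoints.

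**What to change.** Amend SAP 11.4.1 before the blind is broken (SAP 4.3 places that after database lock):

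1. State on which side a count equal to the median falls, and take one cut-off from the pooled arms. Choose the side with the denominator in mind: at the planning mean and SD, high as strictly above the median leaves 8% of patients, about 2 per arm, too few to compare.
2. Compare responders among high-baseline patients only. Alternatively, use logistic regression adjusted for baseline count, with being in the low category on study as the outcome, since the change of category is impossible for low-baseline patients.
3. Count withdrawal for systemic uveitis therapy as non-response in this analysis.
4. State that patients with no relapse on study are included here, despite the restriction in SAP 5.1.

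The cost is SAP wording and a smaller denominator, about 17 rather than 30 per arm in the example. No new data are needed, and in the scenarios above power rises.
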